Due to slow and low recruitment and following discussions with the NIHR HTA in December 2018, it was decided to terminate the study after 6 month follow-up data collection without reaching the planned recruitment target. Findings based on baseline data and 6-month follow-up will still be relevant for meta-analysis in this research area and to guide wider research in the field with regard to feasibility, study design, implementation and challenges faced in relapse prevention trials. In addition, data from the qualitative and EMA sub studies will lead to enhanced knowledge surrounding relapse prevention and strategies used. Data collection for 6-month follow-up is expected to be complete by June/July 2019. The first draft of the statistical analysis plan (SAP) was drafted in January 2019.

This SAP was written once the decision to shut down the study (December 2018) was made as original endpoints and analyses planned in the study protocol, no longer apply. Indeed, no 12-month follow-up data will be collected. The present SAP is a revised plan for the curtailed trial based on the information in the study protocol V4.1 which was finalised on 8 August 2018. The trial statistician has not seen any trial data apart from recruitment updates and has remained blinded throughout the SAP revision.

Amendments to the objectives, aims and analyses are also necessary as the trial did not reach its expected target sample size (N = 1400), in which the trial was powered for. In total, 235 participants were randomised (105 in the UK and 130 in Australia).

Primary Objective

Original

To determine if providing additional strategies designed to help people cope with temptations to smoke (online Structured Planning and Prompting Protocol [S3P] and/or access to smoking replacement [SR] products) when provided following the successful completion of a smoking cessation programme (i.e. at around 4 weeks post quit), reduce relapse rates at 12 months post quit date.

Curtailed Trial

To determine if providing additional strategies (the number of interventions: 0 (UC) vs. 1 (SR or S3P) vs 2 (SR+S3P)) designed to help people cope with temptations to smoke when provided following the successful completion of a smoking cessation programme, reduce relapse rates at 6 months post quit date. See page 13 for full details.

Secondary Objectives

Original

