- Users of the SSS in the UK and the Quitline in Australia who are abstinent in the last 2 weeks of treatment (treatment period is typically 4 weeks post QD) and are still abstinent at point of recruitment. Additionally, in Australia, ethics permission was secured to recruit those quit between 7 and 100 days, and recruit from two additional sources: social media (via Facebook advertising) and St Vincent's Hospital, Melbourne.
- Willing to use a smoking replacement product or online behavioural support tool if allocated to use
- Aged 18 years and older
- Own a mobile phone
- Has Internet access
- Able to read/write/understand English

Exclusion Criteria

[figure not shown]
- Enrolled in other smoking cessation/relapse prevention research
- Currently using EC/oral NRT and planning to use for longer than 3 months

Study Design

[figure not shown]
This is a factorial randomised controlled trial with two comparisons added to usual care (UC; UC is generally 8-12 weeks of pharmacotherapy (e.g. varenicline or NRT), plus standard counselling provided from the commencement of the quit attempt), augmented by a series of text messages available in all conditions. Participants will be individually randomised to one of four arms: UC (Usual Care), SR (Smoking Replacement), S3P (Structured Planning and Prompting Protocol), or SR plus S3P.

Study Scheme Diagram

The study scheme below outlines the flow of participants through the trial and key time points for the original trial and curtailed trial.

Curtailed trial

Randomisation Procedures

Participants were randomised (stratified by country in permuted blocks of random size) to one of four study arms described in the Schedule of Intervention below. The randomisation ratio was 1:1:1:1 across the 4 study arms. Randomisation was done automatically via Stata code with the results imported into the web based program (Quest Engage) that directed the baseline study questionnaire, and occurred after all key baseline information was collected. The 4 arms are described as follows:

- 1. UC arm (control group, receives neither intervention):** If used as part of UC, this group will be encouraged to continue use of base medication (e.g. varenicline or patch) until the end of the recommended period of use.

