- Demographic details, smoking measures (e.g. heaviness of smoking index referenced to when they were smoking [21] information regarding previous quit attempts) and medical history (e.g. screening for depression, measures of perceived stress and affect)
- Information regarding the current quit attempt (including type of support/medicines used), frequency and strength of cravings, extent of slipups if any, plans on how long to continue use of base medication, self-efficacy for maintenance, perceived challenges, number of smokers in social network

All follow ups:

- Self-reported smoking status and cigarette consumption
- Detailed lapse/relapse report for those relapsing (e.g. no. of lapses, when, where, reasons, how many cigarettes at first lapse, how soon after first cigarette was full relapse)
- Strategies used to prevent relapse
- Cravings to smoke
- Participants who stop using SR/S3P/UC will be asked their reasons for doing so (if using at previous survey).
- Use of any, including non-allocated, smoking cessation/relapse prevention treatments
- Detailed use of SR/S3P/UC and ratings of the interventions, including helpfulness (3 month only) and adverse events.

12-month follow up additions – not available in the curtailed trial:

Saliva sample collection for those abstinent at 12 months. Cut off for abstinence is cotinine < 15 ng/ml [22] for those not reporting using any nicotine product and anabasine < 1 ng/ml [23] for those reporting other forms of nicotine use

- European Quality of Life-5 Dimensions (EQ5D) questionnaire
- Health Service Use Questionnaire
- Consumption of alcohol (binge drinking), including changes in consumption [24]).

Routinely collected data:

Use of the S3P will be collected by capturing data on the number of log-ins, number of assessments completed and number of text messages received.

Original Sample Size

We expect 70% of participants to relapse between 1-12 months in UC [25], and that each RP intervention will reduce the rate to 58%, and to 48% in those receiving both. Under these assumptions and comparing those who receive (2 arms) and do not receive (2 arms) each intervention individually, 257 participants are needed

per arm to detect a difference with 90% power ($\alpha=0.025$). We planned to recruit 350 in each arm, for the primary analysis, maximizing power, but retaining sufficient power if there is evidence that participation in the EMA study may have affected outcomes and these participants need to be excluded.

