All analyses will be conducted using a logistic regression where relapse status is regressed onto an ordinal predictor which codes the number of active interventions assigned (0, 1, or 2) adjusted for the stratified (i.e. country). A likelihood ratio test will be conducted initially to assess whether the ordinal predictor should be modelled as continuous or categorical. If the treatment effect is positive, we will also explore the moderating role of country on the treatment effect by including an interaction term between 'treatment' and country. Estimates and 95% confidence intervals will be presented.

Sensitivity analyses of the primary outcome

To assess the robustness of the results, a series of sensitivity analyses will be conducted using different approaches to impute missing information; specifically, we will use multiple imputation by chained equation [26] and complete case analysis where we exclude cases with missing outcomes. To build the multiple imputation model, we will explore differences in baseline measures between participants with complete and missing outcome measures.

Sensitivity analyses will also explore alternative definition of sustained abstinence for the primary outcome, e.g. Russel standard defined as not smoking more than 5 cigarettes since 2-weeks post quit.

Lastly, per protocol analysis will also be conducted to exclude those participants who were not using their allocated product. This will allow us to assess the robustness of the results following departures from the randomised treatment.

No statistical testing (p -value) will be reported for the sensitivity analyses as we are mostly interested in assessing how robust the results are.

All analyses will be carried out in Stata.

Number needed to treat

The number needed to treat (95%CI) for one additional person not to relapse will also be estimated.

Adverse events

The number of adverse events and serious adverse events by study arm will be presented and specific events will be listed.

Tables to be included

- Descriptive statistics of baseline characteristics by study arm.
- Proportion of missing information on the primary and secondary outcomes by study arm.

- Differences in baseline characteristics between patients with complete vs. missing information on the primary outcome.

Figures to be included

- CONSORT diagram

References

1. Ferguson, J., et al., *The English smoking treatment services: one-year outcomes*. *Addiction*, 2005. **100**(s2): p. 59-69.

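### The primary model adjusts for country only and no covariate-adjusted analysis is planned, although potentially prognostic baseline measures were collected before randomisation: a missed efficiency, not an error

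*SAP*

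**What the plan says.** Under Analysis of primary and secondary outcomes, the SAP fits a logistic regression of relapse on the number of interventions assigned, "adjusted for the stratified (i.e. country"). Country is the stratification factor: Randomisation Procedures describes allocation "stratified by country in permuted blocks of random size".

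The baseline list under Curtailed Measures includes the "heaviness of smoking index referenced to when they were smoking", the extent of slip-ups in the current quit attempt, and "self-efficacy for maintenance". Randomisation "occurred after all key baseline information was collected", so these measures precede allocation. Days since quit is not listed by name. It follows from the quit date, which must be known because follow-up is timed from it. Inclusion Criteria adds that "in Australia, ethics permission was secured to recruit those quit between 7 and 100 days".

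The planned sensitivity analyses cover multiple imputation, complete cases, another definition of abstinence and a per-protocol set. None adds baseline covariates to the outcome model. Baseline measures are used for the primary outcome only in building the imputation model.

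**The concern.** The trial stopped far short of its target of 1400: "In total, 235 participants were randomised (105 in the UK and 130 in Australia"). Power is the SAP's own reason for changing the primary comparison. Curtailed Trial Sample Size gives 30% for the original factorial contrasts and 78% for the 0/1/2 coding, and calls the latter optimistic. With recruitment closed, the precision of the analysis is one of the few things still open to improvement.

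In logistic regression, adjusting for pre-randomisation variables that predict the outcome raises the power of the treatment test. If the collected measures predict relapse, a country-only model leaves that gain unused. If they do not, leaving them out saves almost nothing at this sample size. The choice also has to be made before unblinding, because covariates picked afterwards can be suspected of having been chosen for their effect on the result.

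**Working it through.** **Inputs from the SAP.** N = 235, of whom 105 are in the UK and 130 in Australia. "The randomisation ratio was 1:1:1:1 across the 4 study arms", which is 1:2:1 over 0, 1 and 2 interventions. Design relapse rates are 70%, 58% and 48% (Original Sample Size). These are 12-month rates, carried over to the 6-month outcome. Alpha is 0.05 one-sided.

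**Step 1: reproduce the stated 78%.** Trend test with scores 0, 1, 2:
- Mean rate = 0.25×0.70 + 0.50×0.58 + 0.25×0.48 = 0.585. Score variance = 0.5.
- Trend = 0.25×(0.48 − 0.70) = −0.055.
- SE under the null = √(0.585×0.415×0.5/235) = 0.02273.
- SE under the alternative = √[(0.25×0.70×0.30 + 0.25×0.48×0.52)/235] = 0.02211.
- Power = Φ[(0.055 − 1.645×0.02273)/0.02211] = Φ(0.797) = 78.7%.

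This agrees with the stated 78%, a figure that assumes no prognostic covariates. At two-sided 0.05, which matches the planned 95% confidence intervals, the same formula gives 68.2%.

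**Step 2: add covariates.** The SAP's logistic model was simulated 6,000 times per setting with a Wald test, using country only and then country plus four baseline covariates. Marginal rates were held at 70/58/48%. The covariates were independent normal variables of equal weight. Their joint strength is assumed, because the SAP gives none. The last two columns count missing outcomes as relapsed, as the SAP does. The 20% and 30% rates, and missingness at random, are assumptions, and the AUC there describes the link before missing outcomes are recoded.

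| Joint AUC | Country only | Plus four covariates | Gain, none missing | Gain, 20% missing | Gain, 30% missing |
|---|---|---|---|---|---|
| 0.50 | 77.1% | 77.3% | about 0 | – | – |
| 0.61 | 79.4% | 80.6% | about 1 | 0.7 | 0.5 |
| 0.68 | 78.6% | 81.9% | about 3 | 2.5 | 2.0 |
| 0.74 | 77.6% | 84.3% | about 7 | 4.0 | 2.6 |
| 0.79 | 78.4% | 87.3% | about 9 | 5.9 | 3.8 |

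Gains are in percentage points, one-sided 0.05. The simulation error of one power figure is about √(0.78×0.22/6000) = 0.5 points. At two-sided 0.05 the gain is about 0 to 12 points with none missing and about 1 to 8 with 20-30% missing. Under the null, the adjusted test rejected in 4.6% and 5.0% of runs at a nominal one-sided 5%, so its level was kept.

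**Step 3: why days since quit could matter.** Appendix 1 scores relapse from the previous survey onwards. Taking 6 months as 183 days, an Australian entrant at day 7 is at risk for 183 − 7 = 176 days, and one at day 100 for 183 − 100 = 83 days. For illustration, assume a constant hazard that gives 60% relapse from day 30 to day 183:
- Hazard = −ln(0.40)/153 = 0.00599 per day.
- Day 7: 1 − exp(−0.00599×176) = 65%.
- Day 100: 1 − exp(−0.00599×83) = 39%.

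If the overall figure is 50%, the pair is 55% and 31%. If it is 70%, the pair is 75% and 48%. These are the ends of the window. The SAP does not give the actual spread of entry times.

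**The case against.** The strongest reply is that nothing here is wrong. Stratifying by country and adjusting for country is consistent, pre-specified and valid. That stands: this is an efficiency left unused.

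A reader might infer that the baseline measures are known to be strong predictors and that the plan therefore certainly loses power. The SAP does not support that. It reports no prognostic figure for any of them, and a reference title that mentions prediction gives no strength. Two candidates also have limits. Entry requires abstinence in the last two weeks of treatment and at recruitment, which may leave little variation in slips. The 7-100 day window applies to Australia only, so the country term absorbs part of the variation in days since quit. It cannot absorb the variation among the Australian participants, and that part of the argument rests on the SAP itself.

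The rule that missing means relapsed weakens the link between covariates and outcome, and the working allows for this. Adjustment also makes the odds ratio conditional, which matters for a trial whose results are meant for meta-analysis and which reports a number needed to treat. That is a fair cost, and the change has to deal with it.

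Chance imbalance is sometimes added as a further argument. Randomisation-based inference already allows for it, and adjustment addresses only the covariates modelled, so this point does not rest on it.

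**Conclusion.** The point holds as a cheap improvement that is useful only if made before unblinding. The expected gain is about 0 to 9 points of one-sided power, or about 0.5 to 6 if 20-30% of outcomes are missing and counted as relapsed. The result depends on the assumed joint AUC, on the design relapse rates holding at 6 months, and on missingness at random. The downside in power is negligible (77.1% against 77.3% with useless covariates).

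A reader might also infer that the country-only result would be invalid, or that adjustment would rescue the trial. Neither follows. The country-only test is sound. The 30% power for the factorial contrasts, and the fall from about 78% to about 68% when the ordinal test is taken two-sided, are larger limitations than this one.

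**What to change.** Before unblinding, amend Analysis of primary and secondary outcomes as follows:
- Fix the primary model's covariates: country, heaviness of smoking index, log days since quit at randomisation, self-efficacy for maintenance, and any slip since quitting (yes/no) if it varies enough. State the coding of each, and decide whether slips enter from pooled data, blind to arm and outcome.
- Impute missing baseline values singly, without using arm or outcome.
- From the fitted model, obtain a marginal risk difference by standardisation over all randomised participants. Use it for the number needed to treat, and name the contrast it refers to.
- Report the country-only estimate with its 95% confidence interval beside the adjusted one, for meta-analysis.
- Say whether the covariates also apply to the secondary outcomes, since the SAP describes one model for all analyses.

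The cost is SAP wording and a little programming. No new data are needed. The one real downside is the conditional odds ratio, which the standardised risk difference and the country-only estimate address. If unblinding has already taken place, the adjusted model should be reported only as a supportive analysis and labelled as such.

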Curtailed Trial Sample Size

The analysis plan is for the curtailed trial. The study was originally powered to be able to assess the effectiveness of the SR and S3P interventions (main effects); SR (2 arms) vs. no SR (2 arms) & S3P (2 arms) vs. no S3P with power = .90 and $\alpha = 0.025$.

With a final sample size of 235 and using $\alpha 0.025$, we have 30% power to detect a difference between arms (i.e. S3P vs no S3P or SR vs no SR), if one really exists. If we wanted to compare the 4 arms simultaneously in 1 model, the analysis would have 51% power with $\alpha 0.05$ (one-sided).

An alternative approach is to consider the study arms as an ordinal measure where participants are allocated to 0 (UC), 1 (S3P or SR arm), or 2 interventions (S3P+SR). We can assess whether the number of interventions received affects continued abstinence. With a final sample size of 235 and $\alpha = 0.05$ one-sided we have 78% power and this would also avoid multiple testing. We expect the intervention to be more effective at 12 months and, therefore, this is an optimistic power estimate but we can't estimate to what degree.

Overall, the latter approach offers us a viable option to explore differences in therapy on smoking relapse. The revised analyses for the curtailed trial will be useful for future meta-analysis looking at the impact of smoking replacement and/or Structured Planning and Prompting Protocol (S3P) on relapse.

ANALYSIS PLAN

Descriptive statistics

Participants' characteristics at baseline and follow-up will be presented broken down by all 4 arms using appropriate descriptive statistics; mean and standard deviation for continuous measures that are approximately symmetric; median and quartiles if they are skewed distributions. Discrete outcomes should be described using both the number and proportion (percentage). Similarly, summary measures of the primary (i.e. quit rates) and secondary outcomes by arms will also be presented.

Analysis of primary and secondary outcomes

Analyses for the primary and secondary outcomes will use the intention-to-treat (ITT) approach. All participants will be included in the analysis and will be analysed according to the treatment group to which they were randomised. All participants with missing outcomes at six months will be considered to be smoking (relapsed) as per Russell Standard, and to have not reduced their number of cigarettes smoked per day from baseline.

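### A likelihood ratio pre-test on the outcome data picks the primary model, with neither its level nor the categorical-branch test stated, so the claim to avoid multiple testing is not secured

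*SAP*

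**What the plan says.** Under Curtailed Trial Sample Size the SAP compares three analyses of the 235 participants. The two main effects have 30% power at alpha 0.025, and the four-arm comparison has 51%. For the ordinal predictor at alpha 0.05 the text reads "one-sided we have 78% power and this would also avoid multiple testing". The SAP adopts the ordinal approach on these two grounds.

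Under Analysis of primary and secondary outcomes the model is a logistic regression of relapse on the number of assigned interventions, adjusted for country. The next sentence is "A likelihood ratio test will be conducted initially to assess whether the ordinal predictor should be modelled as continuous or categorical". The section gives no significance level for this test. It does not say what is tested if the categorical form is chosen: a 2-df test, 1 versus 0, 2 versus 0, or several of these. On reporting it says only "Estimates and 95% confidence intervals will be presented". One-sided testing is mentioned in the power text and not here.

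**The concern.** The sample size section chooses one 1-df test, and the analysis section makes that choice provisional on the outcomes. A preliminary test that selects the model from the same data is part of the inferential procedure. Fixing the rule in advance does not hold the overall error at 5% unless the whole procedure is calibrated to do so.

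Three things are at stake: control of the primary type I error, the stated benefit of a single test, and knowing before unblinding whether the result is one odds ratio per added intervention or two separate contrasts. The last matters because the SAP offers the results for future meta-analysis.

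**Working it through.** **Inputs.** From the SAP: N = 235, with 105 in the UK and 130 in Australia (Early termination and curtailed trial); "The randomisation ratio was 1:1:1:1 across the 4 study arms" (Randomisation Procedures), so about 58.75/117.5/58.75 people have 0/1/2 interventions; relapse 70/58/48% (Original Sample Size, 12-month assumptions). Missing outcomes count as relapse, so all 235 are analysed. Assumed, because the SAP is silent: a pre-test level of 5% (10% as a variant), several rules for the categorical branch, and a common null relapse rate of 50%, 58.5% or 70%.

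**Step 1: reproduce the stated power.** Trend test with scores 0, 1, 2 (mean score 1).

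- Expected statistic: 58.75 × (0.70 − 0.48) = 12.925. The middle group has weight zero.
- Pooled rate: 0.25 × 0.70 + 0.50 × 0.58 + 0.25 × 0.48 = 0.585.
- Null SD: √(0.585 × 0.415 × 117.5) = 5.341.
- SD under the alternative: √(58.75 × (0.70 × 0.30 + 0.48 × 0.52)) = 5.196.
- One-sided 0.05: Φ((12.925 − 1.645 × 5.341)/5.196) = Φ(0.797) = 78.7%, against 78% stated.
- Two-sided 0.05: Φ((12.925 − 1.960 × 5.341)/5.196) = Φ(0.473) = 68.2%.

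The other figures also reproduce. Main effects (0.64 versus 0.53, 117.5 per side, two-sided 0.025) give 29.7% against 30%. The four-arm 3-df test at 0.05 gives 50.9% against 51%. The 78% is therefore the power of the 1-df trend.

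**Step 2: type I error of the two-stage rule.** There were 100,000 simulated trials per scenario, with the 0/1/2 groups at 26/53/26 in the UK and 32/66/32 in Australia and country-adjusted logistic models. The Monte Carlo standard error near 7% is √(0.07 × 0.93/100,000) = 0.08 points. Ranges run over the three null rates.

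| Rule in the categorical branch | Pre-test 5% | Pre-test 10% |
|---|---|---|
| 2-df test at 5%; linear branch one-sided | 7.2–8.1% | 7.5–8.1% |
| Either contrast with usual care, one-sided 5% | 6.4–7.2% | 7.1–7.9% |
| 2 versus 0 only, one-sided 5% | 4.8–5.7% | 4.9–5.6% |
| 2-df test at 5%; linear branch two-sided 5% | 7.0–7.5% | 7.4–7.7% |

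The fixed one-sided trend alone has 4.8–5.7% in the same simulations.

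**Step 3: the mechanism.** At a null rate of 70% with a 5% pre-test, the pre-test picks the categorical model in 5.24% of trials, and the 2-df test then rejects in 50.9% of them. The total is 0.9476 × 0.0480 + 0.0524 × 0.5094 = 0.0455 + 0.0267 = 7.2%. The conditional rate is high because a departure statistic already above 3.84 supplies most of the 5.99 that the 2-df test needs. Testing only 2 versus 0 avoids this. With a 1:2:1 split the trend is essentially that contrast (step 1), so it is nearly independent of the pre-test.

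**Step 4: power at 70/58/48%.** The pre-test picks the categorical model in 5.95% of trials, and the 2-df test rejects in 93.2% of those. Overall power is 0.9405 × 0.7955 + 0.0595 × 0.9319 = 0.748 + 0.055 = 80.4%, against 79.6% for the fixed trend in the same simulation.

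**Step 5: the pre-test as a safeguard.** At the 5% level it detects 70/58/58% in 17.1% of trials, 70/55/55% in 23.7% and 70/70/48% in 38.5%.

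**The case against.** The inflation is not a property of the SAP as written. It appears only once a pre-test level and a branch rule are supplied, and one reasonable rule (2 versus 0, one-sided) shows none. This stands, so the error statement has to be a conditional range. Setting the first row of the table against a one-sided 5% also mixes directions, because the 2-df test counts harmful patterns too. A separate simulation without country (200,000 trials) gave 5.9–6.5% when a categorical-branch success also required two interventions to beat usual care. That is smaller, but still above 5%.

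A reader might infer a loss of power, since the 2-df test has 57.5% at the planning rates against 78% for the trend. The documents do not support this. The 57.5% is averaged over all trials, and among those that reach the categorical branch the test rejects in about 93%. Overall power is not reduced.

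A reader might also blame the pre-test for the vague NNT. The sentence "The number needed to treat (95%CI) for one additional person not to relapse will also be estimated" names no comparison in either branch, and a fixed linear model would not supply one, so that is a separate matter.

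Finally, the trial stopped at 235 of 1400, the linearity check is pre-specified with the statistician blinded, and outcomes are tabulated for all four arms regardless. These points limit the damage. They do not remove it: the primary objective is still worded as determining an effect, and p-values are excluded only for the sensitivity analyses.

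**Conclusion.** The point holds as a defect that should be fixed. The SAP lets outcome data select the primary model and leaves open both the pre-test level and the categorical-branch test, so the benefit of avoiding multiple testing is not secured. Depending on the unstated rule, type I error runs from about 5% (no inflation) to about 8%.

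A reader might go further and call the primary p-value invalid. That does not follow, because under one of the open rules the error stays nominal. Nor does the analysis section contain a one-sided decision rule that one branch breaks; it sets no test level or sidedness for either branch. What can be said is that the 78% describes the linear trend only, and that the one-sided level behind it has no counterpart in a 2-df test.

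The figures rest on the assumed pre-test levels, on null relapse rates of 50 to 70%, and on 12-month planning rates used for a 6-month outcome, which the SAP itself calls optimistic.

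**What to change.** Remove the likelihood ratio test as a model selector. State that the single primary analysis is the 1-df linear trend on 0/1/2 interventions, adjusted for country, reported as an odds ratio per additional intervention whatever the fit. Give its alpha and sidedness in the analysis section. If it is two-sided at 0.05, to match the usual reading of a 95% interval, restate the power as about 68%. Report 1 versus 0, 2 versus 0 and the departure-from-linearity test as supportive only.

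The cost is SAP wording, and the SAP says the trial statistician has seen only recruitment updates. There is a small statistical price. If the dose pattern is not linear, the primary estimate is an average slope, which the supportive contrasts will show. With a 70/58/58% plateau the fixed one-sided trend has 38.4% power, against 45.4% for the two-stage rule with a 2-df test, but the latter is bought with the higher type I error shown above.
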